11	Subjects with a diagnosis of any of the following diseases according to DSM-5 
 
a) Neurocognitive disorders
 
b) Schizophrenia spectrum and other psychotic disorders
 
c) Bipolar and related disorders
 
d) Feeding and eating disorders
 
e) Obsessive-compulsive disorder
 
f) Panic disorder
 
g) Posttraumatic stress disorder
 

12	Subjects with a diagnosis of any personality disorders (borderline personality disorder, antisocial personality disorder, paranoid personality disorder, schizoid personality disorder, schizotypal personality disorder, and histrionic personality disorder) according to DSM-5
13	Subjects experiencing hallucinations or delusions, or showing mood-incongruent psychotic features, in the current depressive episode
14	Subjects with a MADRS score of $\geq 5$ for Item 10. Suicide, a Hamilton Rating Scale for Depression (HAM-D) score for suicide (No. 11) of $\geq 3$ , those answering "Yes" to question 4 or 5 of the Columbia Suicide Severity Rating Scale (C-SSRS) at baseline, or those who are, based on current psychiatric symptoms or past medical history, at high risk of suicide during the trial in the opinion of the investigator or subinvestigator
15	Subjects with clinically significant neurological, hepatic, renal, metabolic, hematological, immunological, cardiovascular, pulmonary, or gastrointestinal disorders; subjects can be enrolled if the conditions are mild or well controlled and will not hamper assessment of safety and efficacy.

Table 3.4.3-1 Exclusion Criteria	

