#### **3.8.3.2 Documenting Reasons for Discontinuation**

All subjects have the right to withdraw and the investigator or subinvestigator can discontinue a subject's participation in the trial at any time if medically necessary. In addition, subjects meeting the following criteria must be withdrawn from the trial. Only

one reason for discontinuation (the main reason) can be recorded in the source documents and CRF, along with the date of discontinuation.

- 1) Adverse event:
  - a) Death
  - b) Subject experiences exacerbation of symptoms of the underlying disease, and the investigator or subinvestigator judges that continued participation in the trial is inappropriate
  - c) Subject experiences a change to the manic state
  - d) Based on clinical symptoms, subject is considered to be at high risk of suicide in the opinion of the investigator or subinvestigator or has an MADRS score for Suicidal Thought (No. 10) of  $\geq 5$  or HAM-D suicide score (No. 11) of  $\geq 3$ , or those answering "Yes" to question 4 or 5 of C-SSRS.
  - e) Subject decides to discontinue because of annoyance or discomfort due to a nonserious AE which is not otherwise determined to be an undue hazard
  - f) Continuation of IMP would place the subject at undue risk as determined by the investigator or subinvestigator (eg, there is a safety concern possibly, probably, or likely related to IMP)
    - i) SAE
    - ii) Other safety concern or AE possibly, probably, or likely related to IMP
- 2) Subject's withdrawal of informed consent
  - a) Reasons unrelated to medical condition (issues regarding subject's convenience, such as a change of residence or other commitments: provide detail and review AE history with subject)
  - b) Withdrawal of informed consent (complete written withdrawal of consent form)
- 3) Marked noncompliance with the IMP regimen
  - a) Compliance rate of  $< 65\%$  during the interval between 2 consecutive scheduled visits
- 4) Protocol deviation
  - a) Subject is discovered to have not been in accord with inclusion/exclusion criteria
  - b) Subject has received any prohibited concomitant drugs or therapies, or is judged to be in need of such
  - c) Subject can no longer be administered antidepressant (SSRI or SNRI for rollover subjects and SSRI, SNRI, or mirtazapine for new subjects)
- 5) Lost to follow-up
- 6) Pregnancy (see Section 5.5 Pregnancy)
- 7) Termination of all or part of the trial by the sponsor
- 8) Discontinuation of the trial site by the sponsor

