## 5.2 Eliciting and Reporting Adverse Events

The investigator or subinvestigator will periodically assess subjects for the occurrence of AEs. To avoid bias in eliciting AEs, subjects should be asked the nonleading question: “How have you felt since your last visit?” For all AEs (serious and nonserious) reported by the subject, the event name, start and stop dates, severity, seriousness, relationship to IMP, actions taken regarding IMP administration, and outcome thereof must be recorded in the source documents and CRFs provided by the sponsor. Adverse event and SAE collection is to begin after a subject has signed the ICF.

Use medical terminology in AE reporting. Adverse events should be reported as a single unifying diagnosis whenever possible or, in the absence of a unifying diagnosis, as individual signs or symptoms. Exacerbation or disease progression should be reported as an AE only if there are unusual or severe clinical features that were not present, or experienced earlier, or not expected based on the course of the condition. If a reported AE has worsened in severity or seriousness, it should be reported as a new AE on the CRF.

In addition, the sponsor must be notified immediately by e-mail, in principle, of any IREs according to the procedure outlined below, in [Section 5.3](#) Immediately Reportable Events. Special attention should be paid to recording hospitalization and concomitant medications.

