10.2 Adverse Events

All adverse events (AEs) will be coded by Medical Dictionary for Regulatory Activities (MedDRA) (Ver. 24.0) System Organ Class (SOC) and Preferred Term (PT). Numbers and proportions of subjects with the following AEs will be summarized by SOC and PT. If an AE occurs more than once in the same subject, the severest event will be used in summarization.

- Adverse events occurring after initiation of IMP administration (treatment-emergent adverse events [TEAEs])
- TEAEs by severity
- TEAEs with an outcome of death
- Serious TEAEs
- TEAEs leading to discontinuation of the IMP
- TEAEs occurring in $\geq 2\%$ of subjects in any group
- TEAEs by date of initial onset (1-7, 8-14, 15-28, 29-56, 57-84, 85-112, 113-140, 141-168, 169-196, 197-224, 225-252, 253-280, 281-308, 309-336, 337-364, > 364 , post-trial treatment)

TEAEs potentially causally related to the IMP will also be summarized in the same manner.

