10.2.1 Adverse Events of Interest

Adverse events of interest are defined in Appendix 4. Numbers and proportions of subjects with the following AEs of interest will be summarized by SOC and PT.

- Extrapyramidal AEs
- Neuroleptic malignant syndrome-related AEs
- Rhabdomyolysis
- Seizure-related AEs
- Orthostatic disorder-related AEs
- Suicide/suicide attempt-related AEs
- Oversedation-related AEs
- Hypersensitive symptom-related AEs
- Venous thrombosis
- Blood disorder-related AEs
- Glucose metabolism-related AEs
- Lipid metabolism-related AEs
- Body weight-related AEs
- QT interval prolongation-related AEs

- Manic switch-related AEs
- Prolactin increase-related AEs

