Rash pustular
Rash rubelliform
Rash scarlatiniform
Rash vesicular
Reaction to azo-dyes
Reaction to colouring
Reaction to excipient
Reaction to food additive
Reaction to preservatives
Reactive airways dysfunction syndrome
Red man syndrome
Respiratory arrest
Respiratory distress
Respiratory failure
Respiratory tract oedema
Reversible airways obstruction
Rhinitis allergic
Rhinitis perennial
SJS-TEN overlap
Scleral oedema
Scleritis allergic
Scrotal dermatitis
Scrotal exfoliation
Scrotal oedema
Scrotal swelling
Seasonal allergy
Septal panniculitis
Serum sickness
Serum sickness-like reaction
Shock
Shock symptom
Skin erosion
Skin exfoliation
Skin necrosis

Skin oedema
Skin reaction
Skin swelling
Skin test positive
Sneezing
Solar urticaria
Solvent sensitivity
Status asthmaticus
Stevens-Johnson syndrome
Stoma site hypersensitivity
Stoma site rash
Stomatitis
Streptokinase antibody increased
Stridor
Suffocation feeling
Sunscreen sensitivity
Swelling face
Swelling of eyelid
Swollen tongue
Symmetrical drug-related intertriginous and flexural exanthema
Throat tightness
Tongue exfoliation
Tongue oedema
Toxic epidermal necrolysis
Toxic skin eruption
Tracheal obstruction
Tracheal oedema
Tracheostomy
Transplantation associated food allergy
Type I hypersensitivity
Type II hypersensitivity
Type III immune complex mediated reaction
Type IV hypersensitivity reaction
Upper airway obstruction
Urticaria
Urticaria cholinergic
Urticaria chronic
Urticaria contact
Urticaria papular
Urticaria physical
Urticaria pigmentosa
Urticaria vesiculosa
Urticarial dermatitis
Urticarial vasculitis
Vaccination site dermatitis
Vaccination site eczema
Vaccination site exfoliation
Vaccination site hypersensitivity
Vaccination site photosensitivity reaction
Vaccination site rash
Vaccination site recall reaction
Vaccination site urticaria
Vaccination site vasculitis
Vaccination site vesicles

	Vaccine associated enhanced disease
	Vaccine associated enhanced respiratory disease
	Vaginal oedema
	Vaginal ulceration
	Vasculitic rash
	Vernal keratoconjunctivitis
	Vessel puncture site rash
	Vessel puncture site vesicles
	Visceral oedema
	Vulval eczema
	Vulval oedema
	Vulval ulceration
	Vulvovaginal exfoliation
	Vulvovaginal rash
	Vulvovaginal swelling
	Vulvovaginal ulceration
	Vulvovaginitis allergic
	Wheezing
MANIC SWITCH	Hypomania
	Mania
	Manic symptom
NEUROLEPTIC MALIGNANT SYNDROME	Altered state of consciousness
	Autonomic nervous system imbalance
	Blood creatine phosphokinase MM increased

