CT-8.9.8	Incidence of TEAEs for Hypersensitivity (Safety Analysis Set)
CT-8.9.9	Incidence of TEAEs for VTE (Thrombotic and Embolic Events) (Safety Analysis Set)
CT-8.9.10	Incidence of TEAEs for Haematopoietic/Leukopenia (Safety Analysis Set)
CT-8.9.11	Incidence of TEAEs for Effect on Glucose (Safety Analysis Set)
CT-8.9.12	Incidence of TEAEs for Effect on Lipids (Safety Analysis Set)
CT-8.9.13	Incidence of TEAEs for Effect on Weight (Safety Analysis Set)
CT-8.9.14	Incidence of TEAEs for QT Prolongation (Safety Analysis Set)
CT-8.9.15	Incidence of TEAEs for Manic Switch (Safety Analysis Set)
CT-8.9.16	Incidence of TEAEs for Effect on Prolactin (Safety Analysis Set)
CT-8.10.1	Incidence of TEAEs by MedDRA System Organ Class and Preferred Term, by ADT (Safety Analysis Set)
CT-8.10.2	Incidence of TEAEs by MedDRA System Organ Class and Preferred Term, by Gender (Safety Analysis Set)
CT-8.10.3	Incidence of TEAEs by MedDRA System Organ Class and Preferred Term, by Impact of COVID-19 Pandemic (Safety Analysis Set)
CT-9.1	Listing of Deaths
CT-9.2	Listing of Serious Adverse Events
CT-9.3	Listing of Discontinuation of IMP due to Adverse Events
CT-10.1.1	Mean Change From Baseline in Clinical Laboratory Test Results - Serum Chemistry (Safety Analysis Set)
CT-10.1.2	Mean Change From Baseline in Clinical Laboratory Test Results - Hematology (Safety Analysis Set)
CT-10.1.3	Mean Change From Baseline in Clinical Laboratory Test Results - Urinalysis (Safety Analysis Set)
CT-10.1.4	Mean Change From Baseline in Clinical Laboratory Test Results - Prolactin, by Gender (Safety Analysis Set)
CT-10.1.5	Mean Change From Baseline in Clinical Laboratory Test Results - Other Tests (Safety Analysis Set)
CT-10.2.1	Shift Tables of Clinical Laboratory Test Results - Serum Chemistry (Safety Analysis Set)
CT-10.2.2	Shift Tables of Clinical Laboratory Test Results - Hematology (Safety Analysis Set)
CT-10.2.3	Shift Tables of Clinical Laboratory Test Results - Urinalysis1 (Safety Analysis Set)
CT-10.2.4	Shift Tables of Clinical Laboratory Test Results - Urinalysis2 (Safety Analysis Set)
CT-10.2.5	Shift Tables of Clinical Laboratory Test Results - Prolactin, by Gender (Safety Analysis Set)
CT-10.2.6	Shift Tables of Clinical Laboratory Test Results - Other Tests (Safety Analysis Set)
CT-10.3.1	Incidence of Laboratory Test Values With Potential Clinical Relevance (Safety Analysis Set)
CT-10.3.2	Listing of Laboratory Test Values With Potential Clinical Relevance by Subject (Safety Analysis Set)

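### The manic-switch table is limited to three preferred terms, so a switch that a site records as bipolar disorder could be missed there

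*SAP*

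**What the plan says.** SAP 10.2.1 lists 16 groups of adverse events of interest, among them "Manic switch-related AEs", and states that "Adverse events of interest are defined in Appendix 4". Appendix 4 is a list of preferred terms by category. Its MANIC SWITCH entry has three terms: Hypomania, Mania and "Manic symptom". Section 10.2 codes all events to MedDRA 24.0 preferred terms, 10.2.1 summarises each group by system organ class and preferred term, and CT-8.9.15 in Appendix 5 is the manic-switch table. Section 10.2.1 provides neither for further terms nor for medical review of candidate events.

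On the reporting side, protocol 5.2 says: "Adverse events should be reported as a single unifying diagnosis whenever possible". Separate signs or symptoms are the fallback where no such diagnosis exists. Protocol 3.8.3.2, item 1) c), makes this a reason for mandatory withdrawal, filed under adverse events: "Subject experiences a change to the manic state". It does not say which event term the site should enter. Bipolar disorder is a recognised diagnosis in the protocol: "Bipolar and related disorders" is a DSM-5 exclusion for rollover subjects (criterion 11 c) and for new subjects (criterion 35 c).

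**The concern.** The category is defined entirely by coded terms, and the list is closed. Whether a switch enters CT-8.9.15 therefore depends on the word the site chooses. A psychiatrist who sees a manic episode in a subject enrolled with major depressive disorder may record the episode, or may record the diagnosis that the episode now implies. The first is counted and the second is not.

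An omission of this kind can only lower the count. Change to the manic state is serious enough in this protocol to require withdrawal, and few cases are likely in a trial of this size. The table exists so that a reader need not search the full event tables for such cases.

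**Working it through.** The documents state no figure on this point, so there is nothing to reproduce. The check sets the relevant texts side by side and then shows the scale of one case.

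**Step 1: what the list contains.** MANIC SWITCH has three preferred terms. No bipolar term appears in that category or anywhere else in Appendix 4.

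**Step 2: what a site may enter.**

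| Site's entry for the event | In CT-8.9.15? |
|---|---|
| Mania | Yes |
| Hypomania | Yes |
| Manic symptom | Yes |
| A bipolar disorder diagnosis | No, provided it codes to a term outside the three listed |

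The proviso is an assumption, because the dictionary is not part of the documents.

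**Step 3: how Appendix 4 treats comparable categories.** Other categories list the diagnosis beside the finding. SEIZURES has Epilepsy as well as Seizure. EFFECT ON GLUCOSE has Diabetes mellitus and Type 2 diabetes mellitus as well as Blood glucose increased. EPS has Parkinson's disease as well as Tremor. MANIC SWITCH has no term for the corresponding underlying disorder.

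**Step 4: where the event would still be seen.** A treatment-emergent event coded to a bipolar term would appear in CT-8.2.1 (all such events by system organ class and preferred term) and in listing AE-1. If the study drug was stopped for it, it would also appear in CT-8.6.1 and CT-9.3.

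**Step 5: scale of one missed case.** The inputs are the planning figures in protocol 7.1: about 100 subjects completing 52 weeks and 30 new elderly subjects. They serve only as denominators for illustration. The safety analysis set includes everyone dosed, so its denominator will differ. Assume one switch coded to a bipolar term and none coded to a listed term. The limits are exact (Clopper-Pearson) two-sided 95%. For 0 events the upper limit is 1 − 0.025^(1/n). For 1 event the lower limit is 1 − 0.975^(1/n), and the upper limit is the 0.975 quantile of Beta(2, n − 1).

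| n | Shown with the current list | Shown with bipolar terms added |
|---|---|---|
| 100 | 0/100 (0 to 3.6%) | 1/100, 1.0% (0.03% to 5.4%) |
| 30 | 0/30 (0 to 11.6%) | 1/30, 3.3% (0.1% to 17.2%) |

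The SAP plans no confidence intervals for these tables. They are given here only to show what one case does to the reading.

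**The case against.** The strongest reply is that the reporting rule fits the list. Asking for a unifying diagnosis moves sites from components, such as elevated mood or sleeplessness, to one diagnostic term. Mania and Hypomania are such terms, and Manic symptom covers the fallback. The protocol's own name for the event is a change to the manic state, not a change of lifetime diagnosis. It applies DSM-5 to eligibility and baseline diagnosis and nowhere says that event terms follow DSM-5 classes. All of this stands. A reader might infer from protocol 5.2 that sites will enter bipolar disorder and that the table will undercount. The documents support only that they could.

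A second reply is that nothing is hidden, because the event remains in the tables and listings named in Step 4 and no primary or secondary outcome depends on CT-8.9.15 (the SAP plans none). This also stands. It confines the problem to one grouping table, but it does not make that table complete.

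A third is that a narrow, pre-specified list is a legitimate choice, because a bipolar entry can reflect a history taken again rather than an on-treatment episode. That is a real loss of specificity. It is limited because the table is shown by preferred term, so the added terms can be read separately.

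Finally, a reader might put a percentage on the undercount by dividing one missed case by an assumed number of switches, for example 1/4 = 25% or 1/1 = 100%. That only restates the assumption. The documents give neither the number of switches nor the chance that one is recorded as bipolar disorder, and none missed (0%) is equally compatible with them.

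**Conclusion.** The point holds in conditional form. CT-8.9.15 could omit a switch that the site records as bipolar disorder, because the list is closed at three terms, SAP 10.2.1 has no rule for extending it, and the protocol fixes no event term for the switch. The conclusion rests on two assumptions: that a site words the event that way, and that the entry codes outside the three listed terms. No size can be given beyond the scale of a single case, 0/100 instead of 1/100.

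A reader might also infer that the table must disagree with the number of subjects withdrawn for a manic switch. The documents do not show this. Protocol 3.8.3.2 records one main reason for discontinuation and does not say that sub-item c) is captured separately or linked to an event record. A subject re-diagnosed as bipolar might also be filed under 4) a), as not meeting the entry criteria. The label is a cheap improvement.

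**What to change.** Before database lock, add to the MANIC SWITCH list in SAP Appendix 4 the bipolar disorder preferred terms of the MedDRA version used, with their names confirmed in the dictionary. Keep CT-8.9.15 displayed by preferred term, so that the three present terms and the added ones can be read separately.

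If, and only if, the case report form captures sub-reason 1) c) of protocol 3.8.3.2, add a sentence to SAP 10.2.1 that CT-8.9.15 will be cross-checked against withdrawals for that reason.

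The cost is a few lines in Appendix 4 and, where feasible, one sentence in 10.2.1. The added terms need no new data. SAP version 2.0 already revised wording in 10.2.1, so an edit of this kind has a precedent. The downside is that a bipolar re-diagnosis without an on-treatment manic or hypomanic episode could be counted. A table footnote should say so.

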##### (b) Method

After keeping the subject in a relaxed state, body temperature will be measured and then blood pressure (systolic and diastolic) and pulse rate will be measured in the

supine, sitting, and standing positions in accordance with the measurement methods specified by the trial site. For body temperature, the date and result of measurement will be recorded in the source documents and the CRF. Blood pressure and pulse rate will be measured in the supine, sitting, and standing positions, in this order, after maintaining each position for at least 3 minutes. The date, time, positions, and results of measurement will be recorded in the source documents and the CRF.

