	Blood creatine phosphokinase abnormal
	Blood creatine phosphokinase increased
	Blood pressure abnormal
	Blood pressure decreased
	Blood pressure fluctuation
	Blood pressure increased
	Body temperature increased
	Cardiovascular insufficiency
	Catatonia
	Coma
	Confusional state
	Consciousness fluctuating
	Delirium
	Depressed level of consciousness
	Disorientation
	Dyskinesia
	Dyslalia
	Dysphagia
	Dystonia
	Dystonic tremor
	Extrapyramidal disorder
	Fatigue
	Freezing phenomenon
	Heart rate abnormal
	Heart rate increased
	Hyperhidrosis
	Hyperkinesia
	Hyperpyrexia
	Hypertension
	Hyperthermia malignant

	Hypertonia
	Hyporesponsive to stimuli
	Hypotension
	Labile blood pressure
	Labile hypertension
	Leukocytosis
	Loss of consciousness
	Malignant catatonia
	Muscle enzyme increased
	Muscle necrosis
	Muscle rigidity
	Muscular weakness
	Myalgia
	Myoclonus
	Myoglobin blood increased
	Myoglobin blood present
	Myoglobin urine present
	Myoglobinaemia
	Myoglobinuria
	Necrotising myositis
	Neuroleptic malignant syndrome
	Oculogyric crisis
	Opisthotonus
	Palpitations
	Parkinson's disease
	Parkinsonian crisis
	Parkinsonian rest tremor
	Parkinsonism
	Pyrexia
	Respiratory failure
	Resting tremor
	Rhabdomyolysis
	Salivary hypersecretion
	Serotonin syndrome
	Slow response to stimuli
	Stupor
	Tachycardia
	Tremor
	Unresponsive to stimuli
	Urinary retention
	White blood cell count abnormal
	White blood cell count increased
	Withdrawal catatonia
ORTHOSTATIC HYPOTENSION, DIZZINESS, AND SYNCOPE	Dizziness
	Dizziness postural
	Hypotension
	Orthostatic hypotension
	Presyncope
	Syncope
PROLACTIN	Amenorrhoea
	Amenorrhoea-galactorrhoea syndrome
	Anorgasmia
	Blood prolactin

	Blood prolactin abnormal
	Blood prolactin increased
	Breast discharge
	Breast enlargement
	Breast swelling
	Ejaculation disorder
	Erectile dysfunction
	Female orgasmic disorder
	Female sexual dysfunction
	Galactorrhoea
	Gynaecomastia
	Hirsutism
	Hyperprolactinaemia
	Hypomenorrhoea
	Lactation disorder
	Libido decreased
	Loss of libido
	Male sexual dysfunction
	Menstrual disorder
	Menstruation delayed
	Menstruation irregular
	Oligomenorrhoea
	Orgasm abnormal
	Orgasmic sensation decreased
	Prolactin-producing pituitary tumour
	Sexual dysfunction
QT PROLONGATION	Cardiac arrest
	Cardiac death
	Cardiac fibrillation
	Cardio-respiratory arrest
	Electrocardiogram QT interval abnormal
	Electrocardiogram QT prolonged
	Electrocardiogram U wave inversion
	Electrocardiogram U wave present
	Electrocardiogram U-wave abnormality

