	Electrocardiogram repolarisation abnormality
	Long QT syndrome
	Long QT syndrome congenital
	Loss of consciousness
	Sudden cardiac death
	Sudden death
	Syncope
	Torsade de pointes
	Ventricular arrhythmia
	Ventricular fibrillation
	Ventricular flutter
	Ventricular tachyarrhythmia
	Ventricular tachycardia
RHABDOMYOLYSIS AND CPK ELEVATION	Acute kidney injury
	Anuria
	Biopsy muscle abnormal
	Blood calcium decreased
	Blood creatine phosphokinase MM increased
	Blood creatine phosphokinase abnormal

Blood creatine phosphokinase increased
Blood creatinine abnormal
Blood creatinine increased
Chromaturia
Chronic kidney disease
Compartment syndrome
Creatinine renal clearance abnormal
Creatinine renal clearance decreased
Diaphragm muscle weakness
Electromyogram abnormal
End stage renal disease
Glomerular filtration rate abnormal
Glomerular filtration rate decreased
Haematoma muscle
Hypercreatininaemia
Hypocalcaemia
Muscle discomfort
Muscle disorder
Muscle enzyme increased
Muscle fatigue
Muscle haemorrhage
Muscle necrosis
Muscle rupture
Muscle strength abnormal
Muscular weakness
Musculoskeletal discomfort
Musculoskeletal disorder
Musculoskeletal pain
Musculoskeletal toxicity
Myalgia
Myalgia intercostal
Myoglobin blood increased
Myoglobin blood present
Myoglobin urine present
Myoglobinaemia
Myoglobinuria
Myopathy
Myopathy toxic
Myositis
Necrotising myositis
Oliguria
Renal failure
Renal impairment
Renal tubular necrosis
Rhabdomyolysis
Subacute kidney injury
Tendon discomfort
Thyrotoxic myopathy
1p36 deletion syndrome
2-Hydroxyglutaric aciduria
Acquired epileptic aphasia
Acute encephalitis with refractory, repetitive partial seizures
Alcoholic seizure
Alpers disease

SEIZURES

Amygdalohippocampectomy
Aspartate-glutamate-transporter deficiency
Atonic seizures
Atypical benign partial epilepsy
Aura
Automatism epileptic
Autonomic seizure
Baltic myoclonic epilepsy
Benign familial neonatal convulsions
Benign rolandic epilepsy
Biotinidase deficiency
CDKL5 deficiency disorder
CEC syndrome
CSWS syndrome
Change in seizure presentation
Clonic convulsion
Congenital bilateral perisylvian syndrome
Convulsion in childhood
Convulsions local
Convulsive threshold lowered
Corpus callosotomy
Deja vu
Double cortex syndrome
Dreamy state
Drop attacks
Drug withdrawal convulsions
Early infantile epileptic encephalopathy with burst-suppression
Eclampsia
Epilepsy
Epilepsy surgery
Epilepsy with myoclonic-tonic seizures
Epileptic aura
Epileptic psychosis
Faciobrachial dystonic seizure

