- CT-7.2 Extent of Exposure to ADT (Safety Analysis Set)
- CT-7.3 Summary of Treatment Compliance (Efficacy Analysis Set)
- CT-8.1 Adverse Events (All Causalities) (Safety Analysis Set)
- CT-8.2.1 Incidence of TEAEs by MedDRA System Organ Class and Preferred Term (Safety Analysis Set)
- CT-8.2.2 Incidence of Drug-related TEAEs by MedDRA System Organ Class and Preferred Term (Safety Analysis Set)
- CT-8.3.1 Incidence of TEAEs by MedDRA System Organ Class, Preferred Term and Severity (Safety Analysis Set)
- CT-8.3.2 Incidence of Drug-related TEAEs by MedDRA System Organ Class, Preferred Term and Severity (Safety Analysis Set)
- CT-8.4.1 Incidence of Deaths due to TEAEs by MedDRA System Organ Class and Preferred Term (Safety Analysis Set)
- CT-8.4.2 Incidence of Deaths due to Drug-related TEAEs by MedDRA System Organ Class and Preferred Term (Safety Analysis Set)
- CT-8.5.1 Incidence of Serious TEAEs by MedDRA System Organ Class and Preferred Term (Safety Analysis Set)
- CT-8.5.2 Incidence of Serious Drug-related TEAEs by MedDRA System Organ Class and Preferred Term (Safety Analysis Set)
- CT-8.6.1 Incidence of TEAEs Resulting in Discontinuation of IMP by MedDRA System Organ Class and Preferred Term (Safety Analysis Set)
- CT-8.6.2 Incidence of Drug-related TEAEs Resulting in Discontinuation From Study by MedDRA System Organ Class and Preferred Term (Safety Analysis Set)
- CT-8.7.1 Incidence of TEAEs of at Least 2% in Any Group by MedDRA System Organ Class and Preferred Term (Safety Analysis Set)
- CT-8.7.2 Incidence of Drug-related TEAEs of at Least 2% in Any Group by MedDRA System Organ Class and Preferred Term (Safety Analysis Set)
- CT-8.8.1 Incidence of TEAEs by MedDRA System Organ Class, Preferred Term and Time to First Onset (Safety Analysis Set)
- CT-8.8.2 Incidence of Drug-related TEAEs by MedDRA System Organ Class, Preferred Term and

	Time to First Onset (Safety Analysis Set)
CT-8.9.1	Incidence of TEAEs for EPS (Safety Analysis Set)
CT-8.9.2	Incidence of TEAEs for Neuroleptic Malignant Syndrome (Safety Analysis Set)
CT-8.9.3	Incidence of TEAEs for Rhabdomyolysis and CPK Elevation (Safety Analysis Set)
CT-8.9.4	Incidence of TEAEs for Seizures (Safety Analysis Set)
CT-8.9.5	Incidence of TEAEs for Orthostatic Hypotension, Dizziness, and Syncope (Safety Analysis Set)
CT-8.9.6	Incidence of TEAEs for Suicidality (Safety Analysis Set)
CT-8.9.7	Incidence of TEAEs for Somnolence (Safety Analysis Set)

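### SAP Appendix 4 leaves Blood pressure decreased and Loss of consciousness out of the orthostatic/syncope category, so the grouped count in CT-8.9.5 may be too low by an unknown amount

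*SAP*

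**What the plan says.** SAP 10.2.1 states that "Adverse events of interest are defined in Appendix 4", so membership of a PT list decides who is counted in each category. Section 10.2.1 names the category "Orthostatic disorder-related AEs". Appendix 4 heads the list "ORTHOSTATIC HYPOTENSION, DIZZINESS, AND SYNCOPE" and puts six PTs in it: Dizziness, Dizziness postural, Hypotension, Orthostatic hypotension, Presyncope and Syncope. Appendix 5 assigns this category to table CT-8.9.5.

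In the same appendix, "Blood pressure decreased" appears once, under NMS (table CT-8.9.2). "Loss of consciousness" appears twice, under NMS and under QT prolongation (table CT-8.9.14).

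Two protocol provisions bear on which term a site writes. Protocol 5.2 prefers one unifying diagnosis wherever possible, and otherwise has events reported, "in the absence of a unifying diagnosis, as individual signs or symptoms". Protocol 3.7.4.3 states: "Blood pressure and pulse rate will be measured in the supine, sitting, and standing positions". This is done at baseline and at each of the 15 later treatment visits from Week 1 to Week 52.

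**The concern.** The category title names hypotension and syncope, but for each of them the list lacks a closely related term. A fall in blood pressure found at a visit may be reported as a sign and not as a diagnosis. A collapse may be reported as loss of consciousness and not as syncope. Whether the subject enters CT-8.9.5 then depends on the reporter's choice of word.

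CT-8.9.5 is the only planned grouped adverse-event table for hypotension and syncope, and the trial enrols a dedicated group aged 65 or older in order to assess safety in the elderly. What is at stake is the completeness of one descriptive safety count. No test, sample size or efficacy result depends on it.

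**Working it through.** No figure in the plan needs reproducing. The check compares the lists, followed by a short counting argument.

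**1. List membership in SAP Appendix 4**

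| PT | Orthostatic | NMS | QT |
|---|---|---|---|
| Hypotension | yes | yes | no |
| Blood pressure decreased | no | yes | no |
| Syncope | yes | no | yes |
| Loss of consciousness | no | yes | yes |

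The lists are not mutually exclusive: Hypotension and Syncope each sit in two of them. Nothing in the structure prevents cross-listing the other two.

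**2. How Appendix 4 treats such pairs elsewhere**

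- The glucose list holds both Hyperglycaemia and Blood glucose increased.
- The prolactin list holds both Hyperprolactinaemia and Blood prolactin increased.
- The NMS list holds Pyrexia with Body temperature increased, Hypertension with Blood pressure increased, and Hypotension with Blood pressure decreased.
- The QT list holds both Syncope and Loss of consciousness.

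So each of the two pairs in question is complete in another category. In the category named for hypotension and syncope, only one member of each pair is present.

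**3. Direction of the effect**

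Let A be the subjects with at least one of the six listed PTs, and B the subjects with at least one of the two omitted PTs.

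- Count as written: |A|.
- Count on the extended list: |A ∪ B| = |A| + |B not in A|.
- Difference: |B not in A|, which lies between 0 and |B|.

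The omission can only lower the count, and only through subjects who have none of the six PTs. A subject who also reports dizziness, for example, is already counted.

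**4. Can the other tables supply the missing number?**

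CT-8.2.1 gives separate PT rows. Subjects can appear in several rows, so adding rows does not give |A ∪ B|. The adverse-event listing AE-1 would allow it to be worked out by hand, but no planned table shows it.

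**5. Do the vital-sign criteria catch the same subjects?**

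Only partly. The orthostatic row of SAP Appendix 1 needs a systolic fall of at least 20 mmHg and also a pulse rise of at least 25 bpm. The low-systolic row needs a value below 90 mmHg with a fall of at least 20 mmHg from baseline. Take a fall from 140 to 105 mmHg on standing without that pulse rise. The drop is 140 − 105 = 35 mmHg, but the pulse condition fails and 105 is not below 90, so neither row is met. Loss of consciousness has no vital-sign counterpart.

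**6. Scale**

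- New subjects aged 65 or older: target 30 treated (SAP section 4). One subject is 1/30 = 3.3 percentage points.
- All subjects: if the target of about 100 completers is met, one subject is at most about 1/100 = 1.0 percentage point.
- As a guide to precision at n = 30, the exact two-sided 95% upper limit is 1 − 0.025^(1/30) = 11.6% for 0/30 and 17.2% for 1/30. The SAP itself plans no confidence intervals.

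The documents give no event rate for either PT, so the expected number of missed subjects cannot be computed.

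**The case against.** The case for leaving the list alone has real force.

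- **No rule is broken.** Section 10.2.1 leaves the definition to Appendix 4 and gives the category an orthostatic label. A deliberately narrow list is possible. This stands: there is no contradiction. The list is not purely orthostatic, however, since Dizziness, Hypotension and Syncope are included with no postural qualifier.
- **Nothing disappears.** All treatment-emergent events are tabulated by PT, separately for new subjects, in CT-8.2.1. At n = 30 one subject (3.3%) passes the 2% threshold for CT-8.7.1. The two PTs also appear in CT-8.9.2, and Loss of consciousness in CT-8.9.14. This stands. A reader might infer that such events go unreported, and the documents do not support that. Only the grouped count is affected.
- **Signs are the fallback.** Protocol 5.2 asks for a diagnosis first, and Hypotension and Orthostatic hypotension are both available. This stands and limits how often the gap will matter.
- **The effect is probably small.** In the overseas trial in elderly subjects (Protocol 1.2.2.5), dizziness occurred in 7.6%, while neither hypotension nor syncope is among the events at 5% or more. Dizziness may well dominate the category. This is a fair expectation, though it comes from another trial.
- **Where to stop?** Blood pressure abnormal, Blood pressure fluctuation, Labile blood pressure and Depressed level of consciousness are also under NMS and not here. The choice does involve judgement. The first three do not state a fall, and the fourth stops short of loss of consciousness, so the two PTs proposed are the closest matches to Hypotension and Syncope.

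A reader might also want to put a percentage on the undercount by assuming what share of falls is coded as the sign. The documents give no basis for such a share. The assumption would simply come back as the answer, and it would ignore subjects already counted through another listed PT.

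**Conclusion.** The point holds as a sensitivity gap. Applied as written, Appendix 4 keeps a subject out of CT-8.9.5 if the only relevant event is coded to Blood pressure decreased or Loss of consciousness. The direction is fixed. The size is unknown and may be zero. It would be an overstatement to call the count biased downward as a fact, since that depends on a coding pattern the documents do not show.

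The conclusion rests on two assumptions: that the lists are applied literally, and that CT-8.9.5 shows the number of subjects with any listed PT as well as the PT rows. The table shells are not in the documents. The consequence is confined to one descriptive table and is most visible in the elderly group. I rate it a cheap improvement, not a defect that threatens the trial's conclusions.

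**What to change.** In SAP Appendix 4, cross-list two PTs in the orthostatic category and keep them where they already are:

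- Blood pressure decreased, to sit beside Hypotension as it already does under NMS.
- Loss of consciousness, to sit beside Syncope as it already does under QT prolongation.

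This takes the list from six PTs to eight. Run CT-8.9.5 on the extended list with PT rows shown, so that a reader who wants the narrower category can see what the two PTs contribute.

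The cost is two lines in an appendix and no new data. The downside is a slightly larger and less specific category, because loss of consciousness can have non-orthostatic causes. Protocol section 7 has the SAP finalised before data lock. If lock has passed, the extended table can be given as a labelled supplementary summary beside the planned one.
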